6.3 Pharmacokinetic Variables

The plasma concentration data may be used in a meta-population pharmacokinetic analysis. The results of the population PK analysis for ESN364 and its active metabolite will be described in separate report.

6.4 Other Variables

Duration of treatment exposure

Duration of exposure to treatment will be calculated in days, using the following formula:

$$\text{Days of exposure} = \text{date of last dose} - \text{date of first dose} + 1$$

Study drug compliance

Study drug compliance will be calculated using the following formula:

$$\text{Study drug compliance} = 100 \times \frac{\text{actual capsules consumed}}{\text{expected capsules consumed}}$$

where

$$\text{Actual capsules consumed} = \text{total capsules dispensed} - \text{total capsules returned}$$

$$\text{Expected capsules consumed} = (\text{last dose date} - \text{first dose date} + 1) \times 2 \text{ capsules per day}$$

Study drug compliance of morning dose

Study drug compliance of morning dose will be calculated using the following formula:

$$\text{Compliance of morning dose} = 100 \times \frac{\text{actual capsules consumed}}{\text{expected capsules consumed}}$$

where

Actual capsules consumed = morning capsules dispensed – morning capsules returned

Expected capsules consumed = (last dose date – first dose date +1) capsules per day

Study drug compliance of evening dose

Study drug compliance of evening dose will be calculated using the following formula:

$$\text{Compliance of evening dose} = 100 \times \frac{\text{actual capsules consumed}}{\text{expected capsules consumed}}$$

where

Actual capsules consumed = evening capsules dispensed – evening capsules returned

Expected capsules consumed = (last dose date – first dose date +1) capsules per day

Diary interaction compliance during the treatment period

Diary compliance during the treatment period will be calculated using the following formula:

$$\text{Diary interaction compliance} = 100 \times \frac{\text{actual diary days with data recorded}}{\text{expected diary days with data recorded}}$$

where

Actual diary days with data recorded = number of diary days with any morning or evening dose or hot flash data recorded from Visit 2 up to and including the last day of exposure to treatment

Expected diary days with data recorded = date of last dose – date of Visit 2 + 1

Previous and concomitant medication

Previous medication is defined as medication with at least one dose taken before the date of the first dose of study drug.

Concomitant medication is defined as medication with at least one dose taken between the date of first dose (inclusive) and the date of last dose (inclusive) of study drug.

7 STATISTICAL METHODOLOGY

7.1 General Considerations

For continuous variables, descriptive statistics will include the number of subjects (n), mean, standard deviation, minimum, median, maximum, 10%, 90%, and lower and upper quartiles. Frequencies and percentages will be displayed for categorical data. Percentages by categories will be based on the number of subjects with no missing data, i.e. will add up to 100%.

Summaries based on FAS and PPS (e.g. disposition, baseline and efficacy data) will be presented by planned treatment group, unless specifically stated otherwise. Safety analysis and other summaries based on SAF will be presented by actual treatment received.

All statistical comparisons will be conducted using two sided tests at the $\alpha=0.05$ significance level unless specifically stated otherwise. All null hypotheses will be of no treatment difference, all alternative hypotheses will be two-sided, unless specifically stated otherwise.

All data processing, summarization, and analyses will be performed using SAS[®] Version 9.3 or higher on Windows[®]. Specifications for tables, figures, and data listing formats can be found in the TLF specifications.

7.2 Study Population

7.2.1 Disposition of Subjects

The following subject data will be presented:

- Number of subjects with informed consent, discontinued before randomization, randomized (overall only);
- Number and percentage of subjects randomized in each analysis set, by treatment group and overall;
- Number and percentage of subjects completed and discontinued the study, by primary reason for study discontinuation for randomized subjects and by treatment group;
- Number and percentage of subjects excluded from PPS4 and PPS12 by reason for exclusion defined in Section [5.3.1](#) and [5.3.2](#) by treatment group for FAS.

7.2.2 Protocol Deviations

Protocol deviations as defined in the Medpace Protocol Deviation Plan will be summarized for all randomized subjects. The number and percentage of subjects meeting any criteria will be summarized for each criterion and overall, by treatment group and total as well as by study site. Subjects deviating from a criterion more than once will be counted once for the corresponding criterion. Any subjects who have more than one protocol deviation will be counted once in the overall summary. A data listing will be provided by site and subject.

The protocol deviation criteria will be uniquely identified in the summary table and listing.

7.2.3 Demographic and Other Baseline Characteristics

Demographic and other baseline characteristics will be summarized by descriptive statistics.

Number and percentage of subjects randomized in each country and site will be presented by treatment group for the SAF.

Descriptive statistics for age, weight, body mass index (BMI) and height at study entry will be presented. Frequency tabulations for sex, ethnicity, and race will be presented. This will be done for the non-randomized subjects, as well as for the SAF and FAS, by treatment group.

Medical history is coded in MedDRA, and will be summarized by System Organ Class (SOC) and Preferred Term (PT) as well as by PT alone, by treatment group for the SAF.

Disease-specific medical history including spontaneous amenorrhea and bilateral oophorectomy will be summarized by treatment group for the SAF. The number and percentage of subjects with amenorrhea <6 months, ≥ 6 - <12 months or ≥ 12 months will be presented by treatment group for the SAF.

Social history (smoking habits) will be summarized by treatment group for the SAF.

7.2.4 Previous and Concomitant Medications

Previous medications are coded with WHO-DD, and will be summarized by anatomic main group (ATC 1st level), therapeutic subgroup (ATC 2nd level), chemical subgroup (ATC 4th level), and preferred WHO name by treatment group for the SAF.

As with previous medications, concomitant medications will be summarized for each treatment group by anatomic main group (ATC 1st level), therapeutic subgroup (ATC 2nd level) and chemical subgroup (ATC 4th level) and preferred WHO name for the SAF. Subjects taking the same medication multiple times will be counted once per medication and investigational period. A medication which can be classified into several chemical and/or therapeutic subgroups is presented in all chemical and therapeutic subgroups.

7.3 Study Drugs

7.3.1 Exposure

The following information on drug exposure will be presented for each treatment group for the SAF:

- Descriptive statistics for cumulative amount of the drug subject was exposed to and average daily dose; and
- Number and percent of subject with dose interruptions by treatment group.

Duration of exposure will be summarized in two ways.

- Descriptive statistics will be presented by treatment group.
- Exposure time will be categorized according to the following categories by treatment group:
 - less than 28 days
 - at least 28 days, less than 57 days
 - at least 57 days, less than 72 days
 - at least 72 days, less than 93 days
 - At least 93 days
 - Unknown.

Counts and percentages of subjects in each of these categories will be summarized for each treatment group for the SAF.

7.3.2 Treatment Compliance

Overall treatment compliance with the dosing schedule, compliance of morning dose, and compliance of evening dose will be examined for subjects in the SAF whose total study drug count and first and last days of treatment are known. Compliance will be calculated compared to the actual treatment period of dosing (first to last day of treatment), not to the planned treatment period.

Percent overall compliance, percent compliance of morning dose, and percent compliance of evening dose will be summarized in two ways for the SAF:

- Descriptive statistics will be presented by treatment group.
- Percent compliance will be categorized according to the following categories by treatment group:
 - Less than 50%,
 - at least 50%, less than or equal to 85%,
 - greater than 85%, less than or equal to 120%,
 - Over 120%, and
 - Unknown.

Overall treatment compliance, compliance of morning dose, and compliance of evening dose through Week 4 will be analyzed in a similar manner.

7.4 Analysis of Efficacy

7.4.1 Analysis of Primary Endpoints

7.4.1.1 Primary Analysis of Co-Primary Endpoints

The primary efficacy analysis will be based on the FAS.

The mean frequency and severity of moderate to severe vasomotor symptoms as well as change from baseline will be summarized by study week and for the last on treatment week. See Section [7.10.6](#) for study week and endpoint derivations. Weekly means will be plotted.

For each of the co-primary efficacy endpoints, an analysis of covariance (ANCOVA) model will be used with treatment group, pooled center, and smoking status (current vs. former/never) as factors, with baseline weight and baseline measurement as covariates. Pooled centers will be generated and documented prior to database lock. The algorithm for pooling centers can be found in Section [7.10.2](#). If the inclusion of pooled centers creates modeling problems, then dropping that factor will be considered.

Pairwise comparisons between the active doses and placebo will be calculated based on least-squares mean contrasts using a 2-tailed 95% confidence interval (CI).

For subjects in the efficacy analysis populations with missing primary efficacy endpoints, multiple imputation by fully conditional specification methods will be used. The multiple imputation model is specified in Section [7.10.1](#).

Since the study design requires the comparison of 7 active dose groups with placebo for 4 co-primary efficacy endpoints, a two-tier closed testing procedure will be used to control the

family-wise error rate. A step-down testing procedure will be followed. The following testing order of doses will be employed:

- a. Placebo versus 90 mg BID (daily dose 180 mg),
- b. Placebo versus 60 mg BID (daily dose 120 mg),
- c. Placebo versus 120 mg QD (daily dose 120 mg),
- d. Placebo versus 30 mg BID (daily dose 60 mg),
- e. Placebo versus 60 mg QD (daily dose 60 mg),
- f. Placebo versus 15 mg BID (daily dose 30 mg), and
- g. Placebo versus 30 mg QD (daily dose 30 mg).

The 4 co-primary efficacy endpoints will be compared at each dose level. If all 4 co-primary efficacy endpoints are statistically significantly better than placebo at a 2-sided alpha level of 0.05 for a given dose this dose level will be considered superior to placebo. A failure to prove the significance for one or more co-primary efficacy endpoints will lead to a failure to demonstrate superiority to placebo at this dose level, and the other dose levels after this one in the sequence will not be tested. In this testing sequence, if one comparison failed to provide the significance at this dose level, the comparisons at other dose levels following this sequence will not be tested.

7.4.1.2 Secondary Analysis of Co-Primary Endpoints

The primary analysis for each of the co-primary endpoints will be repeated using an ANCOVA model with treatment group as a factor and baseline measurement as a covariate.

A supportive analysis will be carried out for the co-primary efficacy endpoints based on the PPS to examine the impact of premature dropouts and/or major protocol deviations. The method used for this analysis will be identical to the primary analysis described in Section [7.4.1.1](#). The missing value imputation method for the early termination might not be applicable for the analysis on PPS since the analysis set only includes completed subjects. Week 4 analyses will be performed on PPS4, and the Week 12 analyses will be performed on PPS12.

An analysis of the primary efficacy variable by week will be conducted with mixed model for repeated measurements (MMRM) on FAS. This analysis will use a restricted maximum likelihood (REML)–based repeated-measures approach. The analyses will include the treatment group, week and smoking status (current vs. former/never) as factors and baseline measurement as a covariate, as well as an interaction of treatment by week and an interaction of baseline measurement by week. An unstructured covariance structure shared across treatment groups will be used to model the within-patient errors. The Kenward-Roger approximation will be used to estimate denominator degrees of freedom and adjust standard errors. The treatment difference will be estimated at all study weeks.

In addition, MCP-Mod analyses as described in the MCP-Mod SAP will be performed on co-primary endpoints.

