For each of the 4 co-primary efficacy endpoints, an analysis of covariance model will be used with treatment group, pooled center, and smoking status as factors, with baseline weight and baseline measurement as covariates. Pairwise comparisons between the active doses and placebo will be calculated based on least-squares mean contrasts using a 2-tailed 95% confidence interval (CI). For subjects in the efficacy analysis populations with missing primary efficacy endpoints, multiple imputation by fully conditional specification methods will be used. The imputation model will use subject demographics (age, sex, race, baseline weight, and smoking status) and baseline and post-baseline mean number and severity of vasomotor symptoms. Sensitivity analyses will be performed with other multiple imputation methods and mixed model for repeat measurements.

Since the study design requires the comparison of 7 active dose groups with placebo for 4 co-primary efficacy variables, a two-tier closed testing procedure will be used to control the family-wise error. A step-down testing procedure will be followed. The following testing order of doses will be employed:

- a. Placebo versus 90 mg BID (daily dose 180 mg),
- b. Placebo versus 60 mg BID (daily dose 120 mg),
- c. Placebo versus 120 mg QD (daily dose 120 mg),
- d. Placebo versus 30 mg BID (daily dose 60 mg),
- e. Placebo versus 60 mg QD (daily dose 60 mg),
- f. Placebo versus 15 mg BID (daily dose 30 mg), and
- g. Placebo versus 30 mg QD (daily dose 30 mg).

The 4 co-primary efficacy endpoints will be compared at each dose level. Only when ESN364 is proved to be significantly better than placebo at a 2-sided alpha level of 0.05 for all 4 co-primary efficacy endpoints will this dose level be claimed to be superior to placebo. A failure to prove the significance for 1 or more co-primary efficacy endpoints will lead to a failure to claim superiority to placebo at this dose level, and the other dose levels after this one in the sequence will not be tested.

The primary efficacy analysis will be based on the FAS. A supportive analysis will be carried out for the co-primary efficacy variables based on the PPAS to examine the impact of premature dropouts and/or major protocol deviations.

Secondary Efficacy Analysis: Efficacy will be further assessed based on the secondary endpoints described above using the FAS.

Safety Analysis

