7.4.2 Analysis of Secondary Endpoints

The analysis of secondary efficacy endpoints will be based on the FAS.

For each of the secondary vasomotor symptom and patient-reported outcome endpoints, an MMRM model as described in Section 7.4.1.2 will be used. The treatment difference will be estimated at all study weeks (week replaced by visit for patient-reported outcome endpoints).

For each of the secondary responder endpoints, logistic regression will be used for the analysis for each week and endpoint. The analyses will include the treatment group and smoking status (current vs. former/never) as factors and baseline measurement (mean frequency of vasomotor symptoms) as a covariate. The missing value will be imputed as a non-responder.

[figure not shown]
For these responder endpoints, the number of subjects who achieve the reduction will be summarized by study week with descriptive statistics for each treatment arm. For 50% and 90% reduction responders, Kaplan-Meier estimate will be used to estimate the time to response and the time to sustained response. Smooth average (SA) will be used for the time to response. SA value for day X-1, day X and Day X+1 would be assigned to day X. The time to response will be the first day with at least 50% (or 90%) response for both original numbers and SA number. The time to sustained response will be the first day with at least 50% (or 90%) response for both original numbers and SA number, and SA response from that day till the end of the treatment at least 50% (or 90%) response on each day. For the non-responders, it will be censored at the end of treatment.

Diary interaction compliance will be summarized with descriptive statistics and presented by treatment group.

Plasma concentrations of hormones and bone turnover markers will be summarized with descriptive statistics for each treatment group at each visit. Additionally, a within-subject change will be calculated as the post-baseline measurement minus the baseline measurement and summarized in the same way. Pharmacodynamic data and efficacy data may be evaluated by a population PD or population PK/PD approach. All details of population analyses will be described in a separate analysis plan and a separate report will be written. When deemed necessary, data from this study may be combined with data from other studies.

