7.10 Handling of Missing Data, Outliers, Visit Windows, and Other Information

7.10.1 Missing Data

If there are no diary entries for a particular calendar day, and the patient reported receiving at least one morning dose of study medication or at least one evening dose of study medication on that day, the frequency of vasomotor symptoms will be imputed to 0; otherwise, the frequency of vasomotor symptoms will be considered missing.

If no vasomotor symptoms were recorded for the day, and the patient reported receiving at least one morning dose of study medication and at least one evening dose of study medication on that day, the severity will be 0.

Missing primary endpoints will be handled by multiple imputation for continuous variables, and non-responder imputation for binary variables.

For study drug compliance, the capsules returned will be imputed to 0 at the visit if no bottle was returned for a visit.

Multiple Imputation Method:

Multiple imputation will be used to impute missing data and will be implemented using SAS® PROC MI. Missing data may be the result of missing Week 4/Week 12 frequency/severity of vasomotor symptoms measurements or the result of patients discontinuing treatment prior to Week 4/Week 12. Missing at random will be assumed.

The imputation model will include the subject demographics (age [$<$ median, \geq median], race [white, non-white], baseline weight [$<$ median, \geq median], and smoking status), and baseline and post-baseline frequency/severity of vasomotor symptoms. Missing data will be imputed 100 times to generate 100 complete data sets. The seed will be 98765. The fully conditional specification method will be used. The 100 complete data sets will then be analyzed using the same analysis method as the one used to analyze the primary endpoint. See Section [7.4.1.1](#). The results from the 100 fitted models will be combined using SAS® PROC MIANALYZE.

If the model fails to converge, exclusion of subject demographics will be considered.

Safety Data Imputation:

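### The MMRM omits baseline weight, and the imputation model splits age and weight at the median, although the primary ANCOVA uses weight as a continuous covariate

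*SAP*

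**What the plan says.** **Primary model.** SAP 7.4.1.1 specifies an ANCOVA with "treatment group, pooled center, and smoking status (current vs. former/never) as factors, with baseline weight and baseline measurement as covariates". Missing endpoints are multiply imputed. SAP 7.10.1 states the assumption: "Missing at random will be assumed".

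**Secondary analyses of the co-primary endpoints.** SAP 7.4.1.2 lists:
- the primary analysis "repeated using an ANCOVA model with treatment group as a factor and baseline measurement as a covariate";
- the per-protocol repeat;
- an MMRM by week, of which it says "The analyses will include the treatment group, week and smoking status (current vs. former/never) as factors and baseline measurement as a covariate". The MMRM also has treatment-by-week and baseline-by-week interactions and an unstructured covariance;
- MCP-Mod analyses, described in a separate SAP.

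**Secondary endpoints.** SAP 7.4.2: "For each of the secondary vasomotor symptom and patient-reported outcome endpoints, an MMRM model as described in Section 7.4.1.2 will be used". The responder logistic model has treatment, smoking and baseline frequency, without weight.

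**Exploratory day and night endpoints.** SAP 7.4.3 returns to the ANCOVA of 7.4.1.1, so these are adjusted for weight and centre.

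**Imputation model.** SAP 7.10.1 uses age and baseline weight each split at the median, race, smoking, and baseline and post-baseline symptom data. The protocol synopsis names age and baseline weight with no split.

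**Role of the MMRM.** The protocol synopsis (Efficacy Analysis) says: "Sensitivity analyses will be performed with other multiple imputation methods and mixed model for repeat measurements". It does not list the MMRM covariates. The SAP gives no reason for the smaller set, and SAP section 8 (changes from protocol) mentions neither the covariates nor the median splits.

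**The concern.** A sensitivity analysis for missing data is easiest to read when it changes the missing-data method and nothing else. Here the primary ANCOVA and the MMRM differ in the handling of missing data and in two adjustment variables. They also condition their missing-at-random assumptions on different sets: the imputation uses age, race, weight and smoking, while the MMRM uses smoking, baseline and the observed weeks. If weight predicts both dropout and outcome, the two results can diverge for that reason alone.

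The same model is the main analysis for every secondary vasomotor and patient-reported endpoint. Those endpoints lose adjustment for a covariate that the sponsor chose for the primary analysis and kept for the exploratory one, and that is recorded at Day 1. Change in frequency and severity at each study week is a secondary endpoint, so the report will carry two estimates of each co-primary quantity, from different covariate sets.

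The median splits add a smaller mismatch: the imputation model is coarser in weight than the ANCOVA fitted to the imputed data.

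**Working it through.** **1. Which planned analyses differ only in missing-data method?**

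| Analysis | Adjustment terms besides treatment | Missing data |
|---|---|---|
| Primary ANCOVA (7.4.1.1) | centre, smoking, weight, baseline | multiple imputation |
| Reduced ANCOVA (7.4.1.2) | baseline | multiple imputation, reading the repeat as keeping it |
| MMRM (7.4.1.2) | smoking, baseline, week, treatment × week, baseline × week | likelihood, MAR |

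- Primary against reduced ANCOVA: only the covariates change. This isolates their effect.
- Reduced ANCOVA against MMRM: at a given week the fixed effects differ by smoking. The imputation's auxiliary variables also differ.
- Primary ANCOVA against MMRM: centre, weight and missing-data method all change.

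No pair isolates the missing-data method exactly. The reduced ANCOVA gets most of the way.

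**2. The plan's own power figures.** Inputs from SAP section 4: 40 per arm, two-sided 5%, two-sample t-test, SD 5 for frequency and 1 for severity. With noncentrality δ = d / (SD × √(2/40)) and 78 degrees of freedom:

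- Frequency differences 3.3 / 3.5 / 4 / 4.5 / 5 give 83.0 / 87.1 / 94.2 / 97.8 / 99.3%. The SAP states 83 / 87 / 94 / 97 / >99%.
- Severity differences 0.64 / 0.75 / 1 give 80.7 / 91.2 / 99.3%. The SAP states 80 / 91 / >99%.

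The stated figures are reproduced to within one percentage point.

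**3. Adding weight alone.** Let R² be the share of the remaining residual variance that weight explains. The residual SD becomes SD × √(1 − R²); the one degree of freedom spent is ignored. The documents give no R². I assume a partial correlation of 0.1 to 0.3, so R² runs from 0.1² = 0.01 to 0.3² = 0.09. At a difference of 3.3:

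| R² | Residual SD | Power |
|---|---|---|
| 0 | 5.000 | 83.0% |
| 0.01 | 4.975 | 83.4% |
| 0.02 | 4.950 | 83.8% |
| 0.05 | 4.873 | 84.9% |
| 0.09 | 4.770 | 86.3% |

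This is a single-week calculation standing in for the MMRM.

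**4. Adding pooled centre as well.** SAP 7.10.2 requires at least 10 subjects per pooled centre, so 352 subjects allow at most 35 levels, or 34 parameters. Designs were simulated with 8 arms of 40 or 44 and 20 to 35 centres. The variance of a pairwise contrast from treatment, baseline and smoking was compared with that from the same model plus weight and centre:

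- Centre not balanced by randomization: variance multiplied by 1.06–1.11 before any gain. The break-even R² is about 0.06–0.10.
- Arms nearly balanced within centre: multiplier about 1.00–1.04, break-even about 0.00–0.03.
- For R² from 0 to 0.20 the SE ratio runs from 0.92 to 1.06 (unbalanced) or 0.90 to 1.02 (nearly balanced).

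Adding centre can raise or lower precision. The SAP describes permuted blocks and no stratification by centre.

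**5. Median split.** For a normally distributed covariate with a linear effect, a median split keeps 2/π = 0.637, about 64%, of the variance that the continuous form explains. This applies only to the imputed part of the data. The SAP assumes about 10% discontinuation.

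**The case against.** The strongest reply is that SAP 7.4.1.2 already supplies a bridging analysis. Its treatment-plus-baseline ANCOVA shows what the covariates do, and only smoking and the auxiliary variables then separate it from the MMRM. A reader might infer from the covariate mismatch that a gap between ANCOVA and MMRM cannot be interpreted at all. The documents do not support that. What remains is that the attribution is not clean, and the bridge does nothing for the secondary endpoints.

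Both methods also rest on missing at random, so matching the covariates would still not test departures from it. That stands.

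A reader might also infer that precision is definitely lost, or that centre belongs in the MMRM too. Neither follows. No document shows weight or centre to be prognostic; inclusion in the primary model is a choice, not evidence of an R². The MMRM already estimates 12 × 13 / 2 = 78 covariance parameters for 12 weeks, and up to 34 centre terms could cost precision or convergence. SAP 7.4.1.1 itself allows centre to be dropped if it causes modelling problems. A leaner repeated-measures model is defensible with respect to centre. The argument is weak for weight, which costs about one degree of freedom.

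In the logistic model, adding weight changes the conditional odds ratio being estimated, and the 90% and 100% responder outcomes may be sparse. That is a fair reason to leave it optional.

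Finally, part of protocol section 10.2.1 is missing from the text available, so a rationale there cannot be excluded. The SAP itself gives none.

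**Conclusion.** The point holds as a minor one. The MMRM omits a covariate used at the primary and exploratory tiers, and the imputation model handles age and weight more coarsely than it needs to. A difference between the primary result and the MMRM cannot be cleanly attributed to missing-data handling, though most of the covariate effect can be separated.

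The possible precision gain on the secondary endpoints is small: 0.4 to 3.3 percentage points of power (83.4 − 83.0 and 86.3 − 83.0). It depends wholly on the assumed R² of 0.01 to 0.09 and on the single-week approximation.

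It would be wrong to read this as a threat to the trial's main conclusion. The testing sequence uses only the co-primary ANCOVAs, so the MMRM does not touch the primary test or its error control. Omitting a covariate does not bias a randomized comparison with complete data; under missing at random it matters only if the covariate predicts both dropout and outcome. The imputation change does feed the primary analysis, but only a small effect is expected at about 10% discontinuation.

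**What to change.** - In SAP 7.4.1.2, add continuous baseline weight as a covariate in the MMRM. Section 7.4.2 inherits the change by reference.
- In SAP 7.10.1, enter age and baseline weight as continuous variables in the imputation model.
- Do not require pooled centre in the MMRM; one sentence saying why it is left out would be enough.
- Treat weight in the responder logistic model as optional.

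The cost is SAP wording, made before database lock and unblinding, and about one degree of freedom in the MMRM. Age is collected at screening and weight at Day 1, so no new data are needed.
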